## 4 Chapter 1: Background Information

### 5 1.1 Introduction

6 The advent of home blood glucose meter (BGM) testing from a fingerstick in the 1980s had a  
7 major impact on the management of diabetes, particularly in individuals using insulin. While  
8 BGMs remain the method of glucose monitoring for most people with diabetes, continuous  
9 glucose monitoring (CGM) systems are now available and have replaced BGM testing for  
10 primary glucose monitoring in an increasing number of adults and children with type 1 diabetes  
11 (T1D) and some with type 2 diabetes (T2D).

12 The CGM device has a sensor that is inserted in the subcutaneous space and measures the  
13 interstitial fluid glucose concentration. Some CGMs, such as the Dexcom G6, provide real-time  
14 glucose measurements every five minutes with alerts for rising or dropping glucose levels and  
15 threshold alarms when a preset hyperglycemia or hypoglycemia level is reached. Other CGMs  
16 such as the Abbott FreeStyle Libre, which also has been referred to as flash glucose monitoring,  
17 show glucose levels only when the user passes the receiver over the sensor to transmit the  
18 glucose data to the receiver; glucose recordings are every 15 minutes.

19 The accuracy of current generation CGMs approaches that of blood glucose meters. For the  
20 current generation of the Dexcom and Abbott sensor, the mean absolute relative difference, a  
21 common metric for assessing accuracy when sensor glucose values are compared with reference  
22 glucose values, is about 10% or lower, which is in about the middle of the range of accuracy of  
23 current blood glucose meters. This accuracy is what led the FDA to approve the device for  
24 non-adjunctive use in dosing insulin.

25 The efficacy of CGM has been demonstrated in randomized trials of adults and youth with type 1  
26 diabetes (T1D), adults with type 2 diabetes (T2D) using insulin, and in a registry of adults  
27 and youth with T1D; including reductions in HbA1c levels, duration of hyperglycemia and  
28 hypoglycemia, and increased time spent with glucose levels between 70 and 180 mg/dL, which is  
29 the target range. Studies not only demonstrated improvement in HbA1c and reduction in  
30 hypoglycemia but also showed that after six months, approximately 90% of individuals were  
31 using CGM on a daily or near-daily basis. CGM users have reported substantial satisfaction with  
32 use of the device and improved quality of life.

33 Studies have demonstrated the benefits of CGM in individuals with T1D or T2D treated with  
34 multiple daily injections of insulin. In the T1D Exchange registry, CGM use  
35 (predominately Dexcom) was associated with lower HbA1c levels irrespective of whether a  
36 pump or injections are used for insulin delivery. Mean HbA1c was 9.1% in individuals not using  
37 a pump or CGM, 8.6% in those using a pump but not a CGM, 7.9% in those using both a pump  
38 and CGM, and 8.0% in those using injections and CGM.

39 Current generation CGMs have been shown to have a good safety profile. The ease of insertion,  
40 lack of need for calibration or routine blood glucose meter testing, and extension of sensor life  
41 have all made the initiation of CGM easier. Thus, the time has come to consider initiation of  
42 CGM use as similar to BGM use.

43 CGM use has been endorsed for individuals with T1D by the American Diabetes Association,  
44 the American Association of Clinical Endocrinologists, the Endocrine Society, and the  
45 International Society for Pediatric and Adolescent Diabetes. Despite these recommendations and

46 the compelling evidence of the benefits of CGM, many individuals with T1D or insulin-using  
47 T2D have not incorporated CGM into their diabetes management. Although there are not specific  
48 data to cite, it is likely that the low rate of CGM adoption partially reflects a lack of awareness  
49 about CGM among primary care providers, who are responsible for the care of not only most  
50 adults with type 2 diabetes but also those with type 1 diabetes. Lack of provider resources to  
51 introduce and incorporate CGM into patient diabetes self-management may also be a limiting  
52 factor to technology adoption, as usage is low even among some leading diabetes centers.  
53 Although demand for endocrinology care continues to grow, access to specialized care may be  
54 impacted by geographic isolation and a shortage in the number of endocrinologists in the United  
55 States.

56 A recently completed feasibility study assessed whether adults with T1D or T2D using insulin  
57 could be trained virtually, outside of the clinic, to initiate and use CGM as part of their diabetes  
58 self-management. This study demonstrated that a virtual approach outside of the clinic can be  
59 used for successful CGM initiation and incorporation into diabetes self-management for adults  
60 with T1D or T2D using insulin. There was a substantial reduction in HbA1c in most participants,  
61 as well as a reduction in estimated mean glucose, with an increase in the amount of time in range  
62 spent with glucose levels between 70 and 180 mg/dL, which is the generally accepted target  
63 range for most adults with T1D or T2D (excluding pregnancy). Further, participant-reported  
64 outcomes evaluated before and after exposure to the virtual clinic revealed improvements in  
65 glucose monitoring satisfaction, confidence in treating hypoglycemia, and reductions in diabetes  
66 distress.

67 It is important for those using CGM to understand how to use the data from the CGM. This  
68 includes looking at patterns and trends to understand what their glucose is doing and how it  
69 changes while sleeping, in between meals, and during periods of exercise and stress.  
70 Understanding CGM data extends beyond responding to alerts and warnings when levels are too  
71 high and too low. Current CGM users may benefit from virtual clinic support to better  
72 understand their CGM data, as not all CGM users meet goals for time in range or HbA1c target.

73 We plan to assess feasibility and efficacy of establishing a virtual diabetes clinic with a focus on  
74 introduction and training related to use of CGM technology and ongoing CGM use to minimize  
75 such rate-limiting factors as geography, cost and access to specialty care. The virtual diabetes  
76 clinic model will include a comprehensive care team with support for diabetes technology such  
77 as CGM and decision support to align with current recommendations in diabetes care. Screening  
78 for and access to diabetes-related mental health support will also be included.

## 79 **1.2 Rationale**

80 The objective of this study is to evaluate a virtual diabetes clinic model, for adults with either  
81 T1D or T2D, that supports integration of CGM into diabetes self-management and evaluates use  
82 of decision support technology within the virtual clinic model. The virtual diabetes clinic model  
83 will also include mental health screening and support services, particularly for diabetes-related  
84 issues.

85 **1.3 Potential Risks and Benefits**

86 **1.3.1 Known Potential Risks**

87 The fingerstick to collect the HbA1c sample could cause bruising and/or pain at the collection  
88 site.

89 The CGM sensor may produce pain when it is inserted into the skin. There is a low risk for  
90 developing a local skin infection at the site of the sensor needle placement. Itchiness, redness,  
91 bleeding, and bruising at the insertion site may occur as well as local tape allergies. On rare  
92 occasions, the sensor may break and leave a small portion of the sensor under the skin that may  
93 cause redness, swelling, or pain at the insertion site.

94 There is a small risk of hypoglycemia when using CGM for insulin dosing if the CGM glucose  
95 value is substantially higher than the true glucose level. There also is a small risk of  
96 hyperglycemia if the CGM glucose is substantially lower than the true glucose.

97 There is a risk of breach of confidentiality. All data will be maintained in a secure database with  
98 restricted access to help assure confidentiality. Data downloaded from diabetes devices will be  
99 collected for the study. Some people may be uncomfortable with the researchers having such  
100 detailed information about their daily diabetes habits.

101 There is the possibility that completion of questionnaires could make the participant feel  
102 uncomfortable.

103 The study may include other risks that are unknown at this time.

104 **1.3.2 Known Potential Benefits**

105 It is likely that the participants will benefit from access to a virtual diabetes specialty clinic and  
106 using CGM in the study. However, it is possible that participants will not directly benefit from  
107 being a part of this study.

108 **1.3.3 Risk Assessment**

109 The protocol risk assessment for this study has been categorized as not greater than minimal risk.

110 **1.4 General Considerations**

111 The study is being conducted in compliance with the policies described in the study policies  
112 document, with the ethical principles that have their origin in the Declaration of Helsinki, with  
113 the protocol described herein, and with the standards of Good Clinical Practice (GCP).

114 **Chapter 2: Study Enrollment and Baseline Data Collection**

115 **2.1 Participant Recruitment and Informed Consent**

116 Adults (age  $\geq 18$  years) with type 1 diabetes or type 2 diabetes using insulin therapy (Tidepool-  
117 compatible pump or injections) will be enrolled. Although the primary focus of the study is to  
118 enroll non-CGM users, CGM users whose glycemic control is suboptimal can be enrolled.  
119 Participation will be limited to U.S. residents in states where the virtual clinic is licensed; state  
120 eligibility will be verified as part of screening. Potential participants may be recruited through  
121 insurance providers, primary care networks, or health care providers. Potential participants also  
122 may become aware of the study by other means, such as another study participant.

123 Up to 800 individuals may sign the informed consent form to initiate screening. Enrollment will  
124 proceed with the goal of at least 300 participants initiating training for CGM use with the Virtual  
125 Clinic. The goal will be to limit T2D enrollment to no more than 100. Recruitment efforts will be  
126 focused on participants who receive diabetes care in a primary care setting rather than through an  
127 endocrinologist, with a goal of having at least 225 who have not seen an endocrinologist in the  
128 past six months. Eligible participants will be included without regard to gender, race, or  
129 ethnicity.

130 The goal will be to include at least 50 participants  $<25$  years of age and at least 50 participants  
131  $>65$  years of age.

132 **2.1.1 Informed Consent and Authorization Procedures**

133 Individuals who indicate that they are interested will be directed to a website with information  
134 about the study. Interested individuals will be able to communicate with study staff who can  
135 answer questions about the study as part of the informed consent process. Individuals who want  
136 to participate in the study will sign the Institutional Review Board (IRB) approved electronic  
137 consent form. As part of the informed consent process, each participant will be asked to sign an  
138 authorization for release of personal information. Participants will be asked to sign an addendum  
139 consent for follow up after the first 6 months if they plan to continue use of CGM.

140 **2.2 Participant Inclusion Criteria**

141 Individuals must meet all the following inclusion criteria in order to be eligible to participate in  
142 the study:

- 143 1. Age  $\geq 18$  years old
- 144 2. Diagnosis of type 1 diabetes or type 2 diabetes and using insulin therapy (at least 3 injections  
145 of insulin per day or insulin pump that is compatible with Tidepool software)  
*146 Multiple daily injection (MDI) users must be willing to enter insulin dosing information  
147 through an app*
- 148 3. See a healthcare provider at least once a year
- 149 4. Resident of United States and plan to reside in the U.S. for the duration of the study  
*150 This requirement is due to virtual clinic license requirements and U.S. use restrictions for  
151 some study software and devices. Not all U.S. states may be eligible for inclusion due to  
152 virtual clinic license status.*

153 5. Use either an Android or iOS smartphone that is compatible with app requirements that are  
154 needed for the study  
155 6. Access to a compatible computer with internet  
156 7. Understand written and spoken English  
157 8. Willing and able to follow the study procedures as instructed

158 **2.3 Participant Exclusion Criteria**

159 Individuals meeting any of the following exclusion criteria at baseline will be excluded from  
160 study participation:

161 1. Current use of a closed loop system where an insulin pump and CGM share information and  
162 insulin dose is automatically adjusted based on glucose reading  
163 2. Current CGM use where Time in Range is  $\geq 60.0\%$  or Time  $< 54\%$  is  $\leq 1.0\%$ .  
164 3. Current use of any off-label glucose-lowering medications for diabetes type (Example: T1D  
165 use of non-insulin, anti-diabetic medications including SGLT2 inhibitors)  
166 *Use of such medications during the study will also be prohibited.*  
167 4. Females who are pregnant, intending to become pregnant, or breastfeeding during the study  
168 5. Current renal dialysis or plan to begin renal dialysis during the study  
169 6. Active cancer treatment  
170 7. Extreme visual or hearing impairment that would impair ability to use real-time CGM  
171 8. Known adhesive allergy/prior skin reaction or skin reaction identified during the blinded  
172 CGM use phase that would preclude continued CGM use  
173 9. Participation in a different diabetes management study during the study  
174 10. Planned relocation to a state other than current state of residence during the study if virtual  
175 clinic is not licensed in the new state.

176 *Individuals working routinely in a state other than current state of residence in the next six  
177 months are also ineligible if the virtual clinic is not licensed in that state.*

178 **2.4 Screening Procedures**

179 Participants will be asked to confirm eligibility by completing a screening questionnaire.  
180 Participants who pass screening will be asked to provide baseline data. Current CGM users will  
181 also be asked to share their CGM data to confirm eligibility. If current data cannot be shared,  
182 current CGM users will be asked to complete blinded CGM data collection. Non-CGM users  
183 will also be asked to complete blinded CGM data collection. Participants will be asked to submit  
184 a baseline HbA1c sample

185 **2.5 Collection of Baseline Data and Testing**

186 After informed consent is signed, baseline data will be collected, including the following:

187 • Contact information  
188 • Date of birth

189 • Demographics  
190 • Height and weight  
191 • Socio-economic information such as education, income, and insurance  
192 • Name and contact information of healthcare provider for diabetes management  
193 • Diabetes history, including diabetes duration, prior management, insulin delivery method,  
194 meal bolus determination method, prior severe hypoglycemia (SH), prior diabetic  
195 ketoacidosis (DKA)  
196 • Medical history  
197 • Medications, including but not limited to medications other than insulin being used for  
198 glycemic control  
199 • Prior CGM experience and knowledge, including why CGM is not used  
200 • General health  
201 • Questionnaires (see Chapter 4)  
202 • Finger stick to measure HbA1c  
203 • Blinded CGM Data Collection

204 **2.5.1 HbA1c**

205 HbA1c will be measured at a central laboratory. The participant will be sent a kit, which will  
206 include a blood collection tube and shipping materials, to obtain a finger stick blood sample. The  
207 sample will be returned to the lab in a prepaid mailer. Participants will be able to view their  
208 HbA1c results through the study website.

209 **2.6 CGM System**

210 Participants will use the Dexcom G6, which is a commercially available CGM system. CGM  
211 data will be shared with CDCES and study team members.

212 Other sensors that become FDA approved during the course of the study may be included as an  
213 option for participants. If additional sensors are included, the participants will be given  
214 information about CGM system options and will review the CGM systems with a study team  
215 member. A recommendation may be provided for one of the systems based on discussion with  
216 the participant, or there may be an indication that there is no specific recommendation.  
217 Participants will be able to select the CGM system that they prefer, regardless of  
218 recommendation. After a CGM system is selected, the participant may be asked why that system  
219 was selected.

220 **2.7 Blinded CGM**

221 Non-CGM users will use a blinded CGM device for a single sensor wear period (usually at least  
222 10 days) prior to CGM initiation. Current CGM users will be asked to use a blinded CGM device  
223 for a single sensor wear period if their current CGM data cannot be successfully shared to  
224 confirm eligibility. Study supplies required for blinded CGM data collection will be sent to the  
225 participant by mail. An Android phone may be provided which is used as a receiver to collect  
226 data from the blinded Dexcom G6 Pro. Current non-Dexcom CGM users, including pump users  
227 with integrated CGM should continue to use their personal CGM for glucose management.

228 A virtual clinic team member will be available to answer questions about blinded CGM use. The  
229 participants will not be able to see the glucose values and will be expected to follow their normal  
230 diabetes management practice during this blinded CGM use period. The goal will be to obtain  
231 ten days of blinded data. Participants may be asked to use a blinded CGM for an additional  
232 sensor wear period if enough CGM data are not available to establish baseline comparator data.  
233 Participants will be dropped from the study if blinded data cannot be obtained. Participants who  
234 have a serious skin reaction to the sensor during blinded CGM wear that precludes continued use  
235 of a sensor will be dropped. If additional FDA-approved CGM options are available for use in  
236 this study, the participant may be offered the opportunity to try the other CGM system; in this  
237 case blinded data collection would be repeated with another system.

238 **2.8 Psychosocial Screening Questionnaires**

239 Separate from the patient-reported outcome questionnaires, psychosocial screening  
240 questionnaires are administered to study participants 4 times during the study: as part of baseline  
241 data collection and 1, 2, and 3 months after unblinded CGM initiation. These screening  
242 questionnaires are validated tools to evaluate depression, diabetes distress, and hypoglycemia  
243 fears. Questionnaire administration is repeated to ensure that the virtual clinic team delivering  
244 diabetes care is aware of any mental health issues that may make diabetes management harder  
245 for the study participant. An elevated score on any of these questionnaires prompts an automated  
246 alert to the virtual clinic team (See section 3.2).

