Protocol Overview/Synopsis	
Patient Population Adults ≥ 18 years with type 1 diabetes or type 2 diabetes using insulin therapy will be enrolled. Although the primary focus of the study is to enroll non-CGM users, CGM users whose glycemic control is suboptimal can be enrolled. Potential participants may be recruited through insurance providers, primary care networks, or health care providers.
 
Baseline Data Collection Baseline data collected will include demographics, height and weight, socioeconomic status, diabetes history, knowledge of and experience with diabetes devices, medical history and medications, and health-related physical activity. Questionnaires will collect information related to hypoglycemia awareness, treatment satisfaction, and psychosocial issues. Participant contact information will be collected. Contact information for the participant's diabetes healthcare provider will also be collected.
 
HbA1c Participant will receive fingerstick HbA1c kits that will be sent to a central lab for measurement after enrollment and at 13 weeks, 26 weeks, 39 weeks, and 52 weeks.
 
Contact between Study Team and Participant Each participant will be assigned to work with virtual clinic team members. Mental health service support options for diabetes-related mental health issues will be discussed as needed.
 
Virtual clinic team members will check in with participants during the initial six months of study follow up to review CGM data and recommendations related to diabetes management. Participants who continue in the optional extended follow-up phase after the first six months can contact the virtual clinic as needed.
 
CGM Use Participants who do not currently use a CGM will use a blinded CGM device for a single sensor wear period prior to CGM initiation. Participants may be asked to use a blinded CGM for an additional sensor wear period(s) if enough CGM data are not available to establish a baseline that can be used as baseline comparator data. Current CGM users will be asked to share their CGM data to confirm that they meet study eligibility criteria and to establish a baseline that can be used as baseline comparator data. Virtual training will include CGM set up, sensor insertion, alerts and alarms, uploading data, and visualizing data.
 
Changes in Insulin Dosing

JAEB CENTER FOR HEALTH RESEARCH

PARTICIPANT AREA	DESCRIPTION

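### As printed, exclusion 2 refuses current CGM users with low time in range and little time below 54, against the plain sense of the enrolment text

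*Protocol*

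**What the plan says.** **The exclusion.** The lead-in to Protocol 2.3 reads "Individuals meeting any of the following exclusion criteria at baseline will be excluded from" the study, so meeting one item is enough. Item 2 covers "Current CGM use where Time in Range is" 60.0% or more, *or* where time below 54 is 1.0% or less. The exclusion list in the Protocol Summary gives the same rule with the same connector and the same inequality. Both places print the 54 threshold with a percent sign.

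**The enrolment text.** The synopsis, under Patient Population, says that "CGM users whose glycemic control is suboptimal can be enrolled". Section 2.1 says that, although the main aim is to "enroll non-CGM users, CGM users whose glycemic control is suboptimal can be enrolled". The Introduction (1.1) gives the reason: virtual clinic support may help such people to better "understand their CGM data, as not all CGM users meet goals for time in range or HbA1c target".

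**How the rule is applied.** Under CGM Use, the synopsis asks current users to "share their CGM data to confirm that they meet study eligibility criteria". Section 2.4 says they will "also be asked to share their CGM data to confirm eligibility". Where sharing fails, section 2.7 has them wear a blinded device "for a single sensor wear period if their current CGM data cannot be successfully shared to" establish eligibility.

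**The unit elsewhere.** The outcome lists in the Protocol Summary and in section 6.3 give the 54 threshold in mg/dL.

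**The concern.** Item 2 reads as if it were meant to keep out CGM users who are already doing well. As printed, it also keeps out users who are doing badly on time in range, provided they spend little time at very low glucose. More time below 54 becomes a condition of entry for a current CGM user, and no other part of the protocol says so.

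This is a binding eligibility rule checked against data, so the wording has consequences whichever way staff read it. If they apply it literally, they turn away people whom the enrolment text, in its plain sense, says can join. If they follow the apparent intent, those enrolments breach a written exclusion. The CGM users who do enter would also be a narrower group than sections 1.1 and 2.1 describe.

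**Working it through.** There is no stated figure to reproduce. The check is the logic of the printed rule, followed by a conversion of its thresholds into time per day.

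**Inputs.** Let TIR be the percentage of time in range and T54 the percentage of time below 54. From item 2, the limbs are TIR ≥ 60.0 and T54 ≤ 1.0, joined by *or*. From the lead-in to 2.3, any one item excludes.

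**Eligibility under item 2 as printed.**

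Eligible = NOT (TIR ≥ 60 OR T54 ≤ 1.0) = (TIR < 60) AND (T54 > 1.0)

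**Test cases.** The same two limbs were run as printed and with the connector, the inequality on T54, or both changed. The alternatives are shown for comparison only; none is preferred.

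| User | TIR | T54 | As printed | *and* for *or* | > for ≤ | Both changed |
|---|---|---|---|---|---|---|
| A | 35% | 0.3% | refused | eligible | eligible | eligible |
| B | 35% | 1.5% | eligible | eligible | refused | eligible |
| C | 65% | 3.0% | refused | eligible | refused | refused |
| D | 75% | 0.5% | refused | refused | refused | eligible |

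User A is refused only under the printed text. A and B have the same time in range, and under the printed text the one with more time below 54 is admitted. A wider grid gives the same pattern: at TIR 40% or 59.9%, users with T54 of 0, 0.5 or 1.0% are refused and those with 1.1 or 3.0% are eligible; at TIR 60% or 75%, all are refused.

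User C shows a further consequence. The printed rule also refuses people with adequate time in range but substantial time below 54. The alternatives disagree about C, and also about B and D, so the intended rule cannot be recovered by logic alone.

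**Time per day at full wear** (1,440 minutes, 24 hours).

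- T54 threshold: 0.010 × 1,440 = 14.4 minutes
- TIR threshold: 0.60 × 24 = 14.4 hours
- User A: 0.35 × 24 = 8.4 hours in range; 0.003 × 1,440 = 4.3 minutes below 54
- User B: 8.4 hours in range; 0.015 × 1,440 = 21.6 minutes below 54

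To pass item 2, a current CGM user must spend less than 14.4 hours a day in range and more than 14.4 minutes a day below 54.

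**Is it a text-extraction fault?** Unlikely. The connector and the inequality agree in two places that are worded and formatted differently: the summary prints 60% with a stray closing bracket, and section 2.3 prints 60.0%.

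**The case against.** The strongest reply is that nothing is strictly contradicted. The enrolment sentences are general and permissive. They say that suboptimally controlled CGM users can join, not that all will, and suboptimal is never given a number. Everyone the printed rule admits has time in range below 60% and more than 1.0% below 54, so everyone admitted fits the sentence. Exclusion lists routinely narrow recruitment text: item 1 refuses closed-loop users whatever their control, and nobody would call that a contradiction. Section 1.1 is background and sets no eligibility rule.

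Much of this stands. The conflict is with the plain sense of the text, a drafting error is an inference, and the printed rule does admit some of the intended group. But item 1 excludes a type of device, whereas item 2 sorts CGM users by glycaemic control, which is the very ground on which the synopsis and section 2.1 let them in. A rule that refuses user A and admits user B is hard to square with a rationale about missed time-in-range or HbA1c goals. If the narrow rule is intended, the enrolment text is too broad, so one of the two needs changing.

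It is also fair that the minutes-per-day figures only restate the thresholds and show no effect on any estimate, and that the documents do not show how the screening form applies item 2. The SAP settles nothing: version 1.0 is based on Protocol 2.0 and excludes real-time CGM use in the previous 12 months. For the same reason, the absence of a CGM-user subgroup from SAP section 12 is weak evidence that the impact is small.

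**Conclusion.** The concern holds. Taken as written, item 2 makes a current CGM user eligible only with time in range below 60% and more than 1.0% of time below 54. That conflicts with the plain sense of the synopsis and section 2.1 and fits poorly with section 1.1. The percent sign on 54 is a separate slip on which this conclusion does not depend.

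The reading of the printed text is certain; that it is a drafting error is only probable. The size is limited. Only current CGM users are affected. They are not the primary focus and have no recruitment target. The number turned away cannot be derived from the documents, and no prevalence is assumed here. The SAP calls all analyses exploratory, the 300 is a convenience sample (Protocol 6.2), and no power or sample-size figure changes. This should be fixed because a binding entry rule should agree with the text it implements, not because it threatens the main results.

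**What to change.** The sponsor should state which connector and which inequality direction it intends in item 2, and make section 2.3 and the Protocol Summary agree with section 2.1, the synopsis and section 1.1. If the printed rule is intended, the enrolment sentences in the synopsis and section 2.1 should be narrowed to match it. In either case the 54 threshold should be given in mg/dL, and the screening form checked against the reconciled rule. Which rule is clinically right is for the sponsor to decide.

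The cost is a one-line change in two places, IRB review and approval of the amendment before it takes effect (Protocol 7.2), and the form check. No extra participants or procedures are needed.

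Separately, and whatever is decided here, the SAP needs updating to the current population. Its section 7.1.1 builds baseline CGM metrics from blinded readings only, which leaves no baseline for current users who share their own data.
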